4.9.6 Determination of Sample Size

It is expected that 30 patients will be eligible to enter this study during the proposed timeframe. This is a pilot study; the TEMPA is a more comprehensive assessment of upper extremity function which we will use in the analysis of this group of patients to evaluate what percentage remain stable (within 20% variation from baseline) and analyze correlations with other measures of upper extremity function (9HPT and patient perception using the UEFI). Therefore, this is not a calculated sample size as there is a lack of historical data available for this population and the modalities of testing we plan to utilize. We do not have historical data to gather estimates for an accurate power calculation. We plan to gather data on 30 patients but will screen up to 35 in case of screen failures or early withdrawals. Even with the limited calculations we believe that we will be able to analyze for a clinically meaningful lack of change (stabilization).

4.10 DATA QUALITY ASSURANCE

Accurate, consistent, and reliable data will be ensured through the use of standard practices and procedures.

5. REPORTING OF ADVERSE EVENTS

5.1 ASSESSMENT OF SAFETY

Specification of Safety Variables

Safety assessments will consist of monitoring and reporting adverse events (AEs) and serious adverse events (SAEs) per protocol. This includes all events of death, and any study specific issue of concern.

Adverse Events

An AE is any unfavorable and unintended sign (including an abnormal laboratory finding), symptom, or disease temporally associated with the use of an investigational medicinal product (IMP) or other protocol-imposed intervention, regardless of attribution.

This includes the following:

• AEs not previously observed in the subject that emerge during the protocolspecified AE reporting period, including signs or symptoms associated with Multiple Sclerosis that were not present prior to the AE reporting period.

- Complications that occur as a result of protocol-mandated interventions (e.g., invasive procedures such as cardiac catheterizations).
- If applicable, AEs that occur prior to assignment of study treatment associated with medication washout, no treatment run-in, or other protocol-mandated intervention.
- Preexisting medical conditions (other than the condition being studied) judged by the investigator to have worsened in severity or frequency or changed in character during the protocol-specified AE reporting period.

Serious Adverse Events

An AE should be classified as an SAE if the following criteria are met:

- It results in death (i.e., the AE actually causes or leads to death).
- It is life threatening (i.e., the AE, in the view of the investigator, places the subject at immediate risk of death. It does not include an AE that, had it occurred in a more severe form, might have caused death.).
- It requires or prolongs inpatient hospitalization.
- It results in persistent or significant disability/incapacity (i.e., the AE results in substantial disruption of the subject's ability to conduct normal life functions).

• It results in a congenital anomaly/birth defect in a neonate/infant born to a mother exposed to the IMP.

• It is considered a significant medical event by the investigator based on medical judgment (e.g., may jeopardize the subject or may require medical/surgical intervention to prevent one of the outcomes listed above).

5.2 METHODS AND TIMING FOR ASSESSING AND RECORDING SAFETY VARIABLES

The investigator is responsible for ensuring that all AEs and SAEs that are observed or reported during the study, are collected and reported to the FDA, appropriate IRB(s), and Genentech, Inc. in accordance with CFR 312.32 (IND Safety Reports).

Adverse Event Reporting Period

The study period during which all AEs and SAEs as described in section 5.1 where the subject has been exposed to a Genentech product must be reported. The Reporting period begins after informed consent is obtained and initiation of any study procedures and ends 30 days following the last administration of study treatment or study discontinuation/termination, whichever is earlier. After this period, investigators should only report SAEs that are attributed to prior study treatment.

Assessment of Adverse Events

All AEs and SAEs whether volunteered by the subject, discovered by study personnel during questioning, or detected through physical examination, laboratory test, or other means will be reported appropriately. Each reported AE or SAE will be described by its duration (i.e., start and end dates), regulatory seriousness criteria if applicable, suspected relationship to ocrelizumab (see following guidance), and actions taken.

To ensure consistency of AE and SAE causality assessments, investigators should apply the following general guideline:

Yes

There is a plausible temporal relationship between the onset of the AE and administration of ocrelizumab, and the AE cannot be readily explained by the subject's clinical state, intercurrent illness, or concomitant therapies; and/or the AE follows a known pattern of response to ocrelizumab; and/or the AE abates or resolves upon discontinuation of ocrelizumab or dose reduction and, if applicable, reappears upon re-challenge.

No

Evidence exists that the AE has an etiology other than ocrelizumab (e.g., preexisting medical condition, underlying disease, intercurrent illness, or concomitant medication); and/or the AE has no plausible temporal relationship to ocrelizumab administration (e.g., event diagnosed 2 days after first dose of ocrelizumab).

Expected AEs are those AEs that are listed or characterized in the Package Insert (P.I.)or current Investigator Brochure (IB).

Unexpected AEs are those not listed in the P.I. or current IB or not identified. This includes AEs for which the specificity or severity is not consistent with the description in the P.I. or IB. For example, under this definition, hepatic necrosis would be unexpected if the P.I. or IB only referred to elevated hepatic enzymes or hepatitis.

Unexpected disease progression defined by increase in 1 point on the upper extremity strength scores in the Pyramidal FSS of the EDSS above baseline subsequently confirmed at repeat assessment 6 months later would imply worsening of upper extremity function and require clinical evaluation.

For patients receiving combination therapy, causality will be assessed individually for each protocol-mandated therapy.

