All Product Complaints *without* an AE should be sent to:

Email: [name] [contact]

It is understood and agreed that the Sponsor will be responsible for the evaluation of AEs/SAEs, AESIs, Special Situation Reports (including pregnancy reports) and Product Complaints (with or without an AE) originating from the study.

These single case reports will be exchanged between the parties as outlined below so that regulatory obligations are met.

Relevant follow-up information should be submitted to Genentech Drug Safety as soon as it becomes available and/or upon request.

Serious adverse events (SAEs), AEs of Special Interest (AESIs), pregnancy reports (including pregnancy occurring in the partner of a male study subject), other Special Situation Reports and Product Complaints (with or without an AE), where the patient has been exposed to the Genentech Product, will be sent on a MedWatch form or CIOMS I form or on Genentech approved reporting forms to Genentech Drug Safety. Transmission of these reports (initial and follow-up) will be either electronically or by fax and within the timelines specified below:

SADRs

Serious AE reports that are related to the Product shall be transmitted to Genentech/Roche within fifteen (15) calendar days of the awareness date.

Other SAEs

Serious AEs that are unrelated to the Product shall be reported to Genentech/Roche via the AE master log at least annually.

AESIs

AESIs shall be forwarded to Genentech/Roche within fifteen (15) calendar days of the awareness date.

Other Special Situation Reports

In addition to all SAEs, pregnancy reports and AESIs, the following other Special Situations Reports should be collected even in the absence of an Adverse Event and transmitted to Genentech within thirty (30) calendar days:

- Data related to the Product usage during breastfeeding
- Data related to overdose, abuse, misuse or medication error (including potentially exposed or intercepted medication errors)
- In addition, reasonable attempts should be made to obtain and submit the age or age group of the patient, in order to be able to identify potential safety signals specific to a particular population

Product Complaints

All Product Complaints (with or without an AE) shall be forwarded to Genentech within fifteen (15) calendar days of the awareness date.

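### Section 5.2 needs two wording repairs: an unnamed day-2 event as the only example of implausible timing, and an AE reporting period that can close before the EOS visit of a patient who stops Ocrevus

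*Combined protocol and SAP*

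**What the plan says.** **Causality.** Under Assessment of Adverse Events in 5.2, for the sake of consistent calls, "investigators should apply the following general guideline". One route to 'Yes' begins "There is a plausible temporal relationship between the onset of the AE and administration of ocrelizumab"; another is that "the AE follows a known pattern of response to ocrelizumab". The routes are joined by and/or. 'No' applies when another cause is evident, pre-existing conditions and underlying disease being among those listed, and/or when "the AE has no plausible temporal relationship to ocrelizumab administration (e.g., event diagnosed 2 days after first dose of ocrelizumab". No other section gives an example of implausible timing.

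**What relatedness controls.** Section 5.3 j: "Serious AE reports that are related to the Product shall be transmitted to Genentech/Roche within fifteen (15) calendar days of the awareness date", whereas "Serious AEs that are unrelated to the Product shall be reported to Genentech/Roche via the AE master log at least annually". The expedited FDA reports in 5.6 and the IRB notice in 6.4 also depend on relatedness, there expressed as possible (or probable) relation, together with unexpectedness.

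**Reporting period.** Section 5.2 opens by making the investigator responsible for ensuring that "all AEs and SAEs that are observed or reported during the study, are collected and reported to the FDA", the IRB and the manufacturer. The period that it then defines "ends 30 days following the last administration of study treatment or study discontinuation/termination, whichever is earlier"; afterwards only SAEs attributed to the treatment are to be reported. Section 3.4 has new AEs evaluated at every visit throughout participation. Sections 4.5.1, 4.6 and 4.7 ask a patient who stops Ocrevus to attend an EOS visit, and 4.5.1 and Appendix A include AE review there. None of them says how soon after stopping that visit must take place.

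**The concern.** A guideline written to make causality calls consistent should not allow both answers for one event. An investigator who takes the day-2 example at face value could answer 'No' on timing alone for an early post-infusion event that also satisfies a 'Yes' criterion. For a serious event, that answer moves the report to the manufacturer from the 15-day route to the periodic log, and it may also affect the FDA and IRB notices.

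The reporting period raises a different problem. The visit schedule collects AEs up to EOS, but the period can already have closed for a patient who stops. An AE elicited at that visit may then have no reporting route, although the opening of 5.2 says that everything observed during the study is reported. Suspected relapse is one such event: Appendix A, note 5, captures it as an AE, and a non-serious relapse first identified after closure would be collected but fall outside the period.

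**Working it through.** The plan gives no figure to reproduce here. The check compares the texts and uses simple date arithmetic.

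**1. Can one event satisfy both limbs?** The 'Yes' limb turns on *onset* and sets no time window. The 'No' example turns on *diagnosis*, at 2 days after the first dose, and names no event. Take an event that begins after the first infusion and is diagnosed on day 2.
- Under 'Yes': it qualifies if its onset is plausible in time and nothing else readily explains it, or if it fits a known pattern of response.
- Under 'No': it matches the example word for word.

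Both answers are open. If the event began before the infusion and was only diagnosed on day 2, the example makes sense and the conflict disappears. The text does not limit itself to that case.

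**2. Consequence for a serious event (5.3 j).** Judged related: 15 calendar days. Judged unrelated: log at least annually. The longest wait for the log is:
- sent yearly, the least frequent that the text allows: 365 days, or 365 − 15 = 350 days beyond the related route;
- sent half-yearly (assumed): 365 / 2 ≈ 183 days;
- sent quarterly (assumed): 365 / 4 ≈ 91 days.

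These are ceilings for one event on one route. The documents give no rate of misattribution.

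**3. When does the reporting period end?** Let L be the day of last administration and T the day of study discontinuation or termination. The clause has two readings:
- the 30 days attach to L only: end = min(L + 30, T);
- the 30 days attach to both: end = min(L, T) + 30.

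Both give an end no later than L + 30.

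**4. Can it close before EOS?** Let V be the day of the EOS visit. Closure precedes the visit whenever V − L > 30 days. Nothing in 4.5.1, 4.6, 4.7 or Appendix A requires V − L ≤ 30.

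**5. What falls in the gap?** After closure, attributed SAEs remain reportable (5.2; 5.3 g). AEs attributed to Ocrevus are followed until resolved (4.5.1, 4.6). Pregnancies are covered to 6 months after the last dose (5.3 f), and AESIs have their own 15-day route (5.3 j). What remains is non-serious AEs and SAEs judged unrelated that are first identified after closure in patients who stop.

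**6. Would ending the period at the last visit be enough?** No. Suppose V = T = L + 10. On the second reading the present text covers up to L + 30, so ending at V would lose days 11 to 30. Taking the later of the present end and V loses nothing on either reading.

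**The case against.** **The example has an innocent reading.** *Diagnosed* is not *onset*, and the example stands beside pre-existing conditions and underlying disease. A condition present before the first dose is the natural meaning. It is also only an illustration in a general guideline, and the known-pattern route to 'Yes' stays open whatever the example says. Which day-2 events are plausibly related depends on the package insert or Investigator Brochure, which are not in the documents. All of this stands. It shows that the sponsor probably meant something sensible, but the text does not limit the example to that meaning.

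**Other routes may catch the event.** The FDA reports in 5.6 are copied to the manufacturer, and their test of possible relation is worded more broadly than a Yes/No call. This stands in part: 5.6 covers only unexpected events and still requires a judgement of relatedness.

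**Four stronger inferences that the documents do not support.**
- *Calendar gaps as the loss.* If EOS falls 3 or 6 months after the last infusion (assumed; neither the infusion interval nor EOS timing is stated), the gap is 91 − 30 = 61 or 183 − 30 = 153 days. These do not measure lost AEs. An infusion is known to be the last only afterwards, so until the stop is recognised the patient is followed and reported on as usual.
- *A contradiction on deaths.* Section 5.1 includes all deaths, and 5.3 b limits them to the reporting period. But 5.1 qualifies its statement as reporting per protocol, so 5.3 b reads as the specific rule beneath a general one.
- *Completers lose coverage too.* The drug is commercial, and an infusion during the study need not be the last. The documents do not settle whether later commercial infusions count as study treatment, but patients who continue past Month 24 are probably unaffected.
- *The two problems compound.* An event 2 days after the first dose cannot be later than 30 days after the last one, so the example does not bear on events after that limit.

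**Conclusion.** Section 5.2 is wrong as written in two separate places, and both should be corrected. First, the example allows an early post-infusion event to be classed 'No' while it meets a 'Yes' criterion. For a serious event this exchanges a 15-day report for a log that may be up to 365 days away. That ceiling assumes a yearly log and a literal reading of the example; how often it would happen cannot be estimated. Second, the period's end does not fit the opening of 5.2, the safety plan in 3.4, or the AE review at EOS. The loss is limited to non-serious AEs and SAEs judged unrelated, first identified after closure in patients who stop. Its size is unknown: the planned sample is 30, and the number who will stop is not given.

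No efficacy result changes. Section 4.9.4 plans only a descriptive AE summary, so the stakes are complete and timely reporting rather than inference. Confidence is medium, because the intended meaning of the example and the timing of early EOS visits are not stated.

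**What to change.** 1. In 5.2, delete the 2-day example, or limit it to a named type of event whose onset must precede exposure.
2. Reconcile the reporting period in 5.2 with the opening sentence of 5.2 and with 3.4, 4.5.1, 4.6, 4.7 and Appendix A, so that it runs to the later of its present end and the subject's last study visit (Month 24 or early EOS). State an end date for subjects who do not attend that visit. Keep the existing rule for attributed SAEs afterwards. The references to the period in 5.1 and 5.3 b then follow without further change.
3. Clerical only: 5.3 b points to Section 5.1.2 for the period, which is defined in 5.2.

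The cost is two wording changes, one corrected cross-reference and a note to the site. The downside is a few more AEs to report, from visits that already exist. No visit or assessment is added.

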5.3 PROCEDURES FOR ELICITING, RECORDING, AND REPORTING ADVERSE EVENTS

Eliciting Adverse Events

A consistent methodology for eliciting AEs at all subject evaluation time points should be adopted. Examples of non-directive questions include:

- "How have you felt since your last clinical visit?"
- "Have you had any new or changed health problems since you were last here?"

Specific Instructions for Recording Adverse Events

Investigators should use correct medical terminology/concepts when reporting AEs or SAEs. Avoid colloquialisms and abbreviations.

a. Diagnosis vs. Signs and Symptoms

If known at the time of reporting, a diagnosis should be reported rather than individual signs and symptoms (e.g., record only liver failure or hepatitis rather than jaundice, asterixis, and elevated transaminases). However, if a constellation of signs and/or symptoms cannot be medically characterized as a single diagnosis or syndrome at the time of reporting, it is acceptable to report the information that is currently available. If a diagnosis is subsequently established, it should be reported as follow-up information.

b. Deaths

All deaths that occur during the protocol-specified AE reporting period (see Section 5.1.2), regardless of attribution, will be reported to the appropriate parties. When recording a death, the event or condition that caused or contributed to the fatal outcome should be reported as the single medical concept. If the cause of death is unknown and cannot be ascertained at the time of reporting, report "Unexplained Death".

c. Preexisting Medical Conditions

A preexisting medical condition is one that is present at the start of the study. Such conditions should be reported as medical and surgical history. A preexisting medical condition should be re-assessed throughout the trial and reported as an AE or SAE only if the frequency, severity, or character of the condition worsens during the study. When reporting such events, it is important to convey the concept that the preexisting condition has changed by including applicable descriptors (e.g., "more frequent headaches").

d. Hospitalizations for Medical or Surgical Procedures

Any AE that results in hospitalization or prolonged hospitalization should be documented and reported as an SAE. If a subject is hospitalized to undergo a medical or surgical procedure as a result of an AE, the event responsible for the procedure, not the procedure itself, should be reported as the SAE. For example, if a subject is hospitalized to undergo coronary bypass surgery, record the heart condition that necessitated the bypass as the SAE.

Hospitalizations for the following reasons do not require reporting:

- Hospitalization or prolonged hospitalization for diagnostic or elective surgical procedures for preexisting conditions
- Hospitalization or prolonged hospitalization required to allow efficacy measurement for the study or
- Hospitalization or prolonged hospitalization for scheduled therapy of the target disease of the study.

e. Assessment of Severity of Adverse Events

The adverse event severity grading scale for the NCI CTCAE (v5 .0 Update current versions) will be used for assessing adverse event severity. Below Table should be used for assessing severity for adverse events that are not specifically listed in the NCI CTCAE.

Adverse Event Severity Grading Scale for Events Not Specifically Listed in NCI CTCAE

Grade	Severity
1	Mild; asymptomatic or mild symptoms; clinical or diagnostic observations only; or intervention not indicated
2	Moderate; minimal, local, or non-invasive intervention indicated; or limiting age-appropriate instrumental activities of daily living ^a
3	Severe or medically significant, but not immediately life-threatening; hospitalization or prolongation of hospitalization indicated; disabling; or limiting self-care activities of daily living ^{b,c}
4	Life-threatening consequences or urgent intervention indicated d
5	Death related to adverse event ^d

NCI CTCAE = National Cancer Institute Common Terminology Criteria for Adverse Events.

Note: Based on the most recent version of NCI CTCAE (v5.0), which can be found at: http://ctep.cancer.gov/protocolDevelopment/electronic_applications/ctc.htm

- a. Instrumental activities of daily living refer to preparing meals, shopping for groceries or clothes, using the telephone, managing money, etc.
- b. Examples of self-care activities of daily living include bathing, dressing and undressing, feeding oneself, using the toilet, and taking medications, as performed by patients who are not bedridden.
- c. If an event is assessed as a "significant medical event," it must be reported as a serious adverse event
- d. Grade 4 and 5 events must be reported as serious adverse events

f. Pregnancy

If a female subject becomes pregnant while receiving ocrelizumab or within 6 months after the last dose of ocrelizumab, a report should be completed and expeditiously submitted to the Genentech, Inc. Follow-up to obtain the outcome of the pregnancy should also occur. Abortion, whether accidental, therapeutic, or spontaneous, should always be classified as serious, and expeditiously reported as an SAE. Similarly, any congenital anomaly/birth defect in a child born to a female subject exposed to the ocrelizumab should be reported as an SAE.

Additional information on any ocrelizumab-exposed pregnancy and infant will be requested by Genentech Drug Safety at specific time points (i.e. after having received the initial report, at the end of the second trimester, 2 weeks after the expected date of delivery, and at 3, 6, and 12 months of the infant's life).

g. Post-Study Adverse Events

The investigator should expeditiously report any SAE occurring after a subject has completed or discontinued study participation if attributed to prior ocrelizumab exposure. If the investigator should become aware of the development of cancer or a congenital anomaly in a subsequently conceived offspring of a female subject who participated in the study, this should be reported as an SAE adequately to Genentech Drug Safety during the follow-up period.

h. Case Transmission Verification of Single Case Reports

The Sponsor agrees to conduct the Case Transmission verification to ensure that all single case reports have been adequately received by Genentech via the Sponsor emailing Genentech a Quarterly line-listing documenting single case reports sent by the Sponsor to Genentech in the preceding time period.

The periodic line-listing will be exchanged within seven (7) calendar days of the end of the agreed time period. Confirmation of receipt should be received within the time period mutually agreed upon.

If discrepancies are identified, the Sponsor and Genentech will cooperate in resolving the discrepancies. The responsible individuals for each party shall handle the matter on a case-by-case basis until satisfactory resolution. The sponsor shall receive reconciliation guidance documents within the 'Activation Package'.

Following Case Transmission Verification, single case reports which have not been received by Genentech shall be forwarded by the Sponsor to Genentech within five (5) calendar days from request by Genentech.

At the end of the study, a final cumulative Case Transmission Verification report will be sent to Genentech.

i. AEs of Special Interest (AESI)

AESIs are a subset of Events to Monitor (EtMs) of scientific and medical concern specific to the product, for which ongoing monitoring and rapid communication by the Investigator to the Sponsor is required. Such an event might require further investigation in order to characterize and understand it. Depending on the nature of the event, rapid communication by the trial Sponsor

to other parties (e.g., Regulatory Authorities) may also be warranted.

Adverse events of special interest for this study include the following:

- Cases of potential drug-induced liver injury that include an elevated ALT or AST in combination with either an elevated bilirubin or clinical jaundice, as defined by Hy's law:
 - \circ Treatment-emergent ALT or AST > 3 \times ULN in combination with total bilirubin > 2 \times ULN
 - \circ $\;$ Treatment-emergent ALT or AST > 3 \times ULN in combination with clinical jaundice
- Suspected transmission of an infectious agent by the study drug, as defined below
 - Any organism, virus, or infectious particle (e.g., prion protein transmitting transmissible spongiform encephalopathy), pathogenic or non-pathogenic, is considered an infectious agent. A transmission of an infectious agent may be suspected from clinical symptoms or laboratory findings that indicate an infection in a patient exposed to a medicinal product. This term applies only when a contamination of the study drug is suspected

j. Adverse Event Reporting

The Sponsor will track all protocol-defined AE and pregnancy reports originating from the Study for the Product.

Investigators must report all AEs, SAEs, AESIs pregnancy reports and special situation reports (if applicable) adequately to Genentech within the timelines described below. The completed Medwatch or CIOMS I form or Genentech approved reporting forms should be faxed immediately upon completion to Genentech at the following contacts:

All protocol-defined AEs, SAEs, AESIs, Special Situation Reports (including pregnancy reports) and Product Complaints *with* an AE should be sent to:

[contact] Email: [name]

All Product Complaints *without* an AE should be sent to:

Email: [name] [contact]

It is understood and agreed that the Sponsor will be responsible for the evaluation of AEs/SAEs, AESIs, Special Situation Reports (including pregnancy reports) and Product Complaints (with or without an AE) originating from the study.

These single case reports will be exchanged between the parties as outlined below so that regulatory obligations are met.

Relevant follow-up information should be submitted to Genentech Drug Safety as soon as it becomes available and/or upon request.

Serious adverse events (SAEs), AEs of Special Interest (AESIs), pregnancy reports (including pregnancy occurring in the partner of a male study subject), other Special Situation Reports and Product Complaints (with or without an AE), where the patient has been exposed to the Genentech Product, will be sent on a MedWatch form or CIOMS I form or on Genentech approved reporting forms to Genentech Drug Safety. Transmission of these reports (initial and follow-up) will be either electronically or by fax and within the timelines specified below:

SADRs

Serious AE reports that are related to the Product shall be transmitted to Genentech/Roche within fifteen (15) calendar days of the awareness date.

Other SAEs

Serious AEs that are unrelated to the Product shall be reported to Genentech/Roche via the AE master log at least annually.

AESIs

AESIs shall be forwarded to Genentech/Roche within fifteen (15) calendar days of the awareness date.

Other Special Situation Reports

In addition to all SAEs, pregnancy reports and AESIs, the following other Special Situations Reports should be collected even in the absence of an Adverse Event and transmitted to Genentech within thirty (30) calendar days:

- Data related to the Product usage during breastfeeding
- Data related to overdose, abuse, misuse or medication error (including potentially exposed or intercepted medication errors)
- In addition, reasonable attempts should be made to obtain and submit the age or age group of the patient, in order to be able to identify potential safety signals specific to a particular population

Product Complaints

All Product Complaints (with or without an AE) shall be forwarded to Genentech within fifteen (15) calendar days of the awareness date.

A Product Complaint is defined as any written or oral information received from a complainant that alleges deficiencies related to identity, quality, safety, strength, purity, reliability, durability, effectiveness, or performance of a product after it has been released and distributed to the commercial market or clinical trial.

REPORTING REQUIREMENTS FOR ADVERSE EVENTS ORIGINATING FROM PATIENT REPORTED OUTCOMES

Although sites are not expected to review the PRO data, if physician/study personnel become aware of a potential adverse event during site review of the PRO questionnaire data, he/she will determine whether the criteria for an adverse event have been met and, if so, these must be reported using the Adverse Event and Special Situation Reporting Form or MedWatch form.

